15.6.5. Pharmacokinetic

This document is intended for planning analysis of PK concentration data and PK parameters only. Population pharmacokinetics and identification of important determinants of variability will be described in a separate document.

| Pharmacokinetic Analyses | | | | | | | | | | | | | | | | | | |
|--|------------------------------|-----------------------|----------------------|---------------|------------------------------|--|--|-------------------|-----------------------|----------------------|-----|------------------|-----------------|-------------------|-----|------------------|-----------------|--------------------|
| Plasma CAB and RPV Concentration-time Data | | | | | | | | | | | | | | | | | | |
| 
Plasma samples for determination of CAB and RPV concentration will be collected throughout the Maintenance Phase, at Week 152 and at the withdrawal visit in the main study, and up to Week 17 in the sub-study. Additional samples will be collected for storage during the Long-Term Follow-Up Phase and for female participants who become pregnant during the study.
 
In rare occasions, PK samples are collected post-dose on the same day as the study treatment administration during the main study. The data from these PK samples will be excluded from the pre-dose and/or 1-week post-dose summaries in the main study. If time was not collected for the oral study treatment, the PK sample collected on the same day as the oral study treatment is assumed to be taken prior to the oral dose unless medical monitor or data querying informs otherwise.
 
PK data collected for liver event will be listed but will not be included in the summaries or figures.
 | | | | | | | | | | | | | | | | | | |
| Plasma CAB and RPV PK Parameters | | | | | | | | | | | | | | | | | | |
| 
The following PK parameters will be determined from the sub-study concentration-time data for each treatment, analyte and dosing interval, as data permit: maximum concentration (Cmax), time to Cmax (tmax), area under the plasma concentration-time curve through the end of the dosing interval (AUC(0-tau)). These PK parameters will be calculated by standard non-compartmental analysis according to current working practices and using Phoenix WinNonlin 8.3. All calculations of non-compartmental parameters will be based on actual sampling times. Derivation of PK parameters will be performed by, or under the direct auspices of, Clinical Pharmacology Modelling and Simulation (CPMS), GlaxoSmithKline.
 
In addition, the concentration at the end of a dosing interval (Ctau) will be obtained from the evaluable pre-dose (trough) concentration collected at start of the subsequent interval. For example, the Ctau for last thigh injection interval will be obtained from the evaluable pre-dose PK concentration collected at the Sub-study Week 16 visit.
 | | | | | | | | | | | | | | | | | | |
| 
  
 Treatment Arm	Dosing Interval in Sub-study	
 
 Gluteal Injection	First Thigh Injection	Last Thigh Injection	
   
 Q8W	Week -8 to Day 1	Day 1 to Week 8	Week 8 to Week 16	
 
 Q4W	Week -4 to Day 1	Day 1 to Week 4	Week 12 to Week 16	
  
 | | | | Treatment Arm | Dosing Interval in Sub-study | | | Gluteal Injection | First Thigh Injection | Last Thigh Injection | Q8W | Week -8 to Day 1 | Day 1 to Week 8 | Week 8 to Week 16 | Q4W | Week -4 to Day 1 | Day 1 to Week 4 | Week 12 to Week 16 |
| Treatment Arm | Dosing Interval in Sub-study | | | | | | | | | | | | | | | | | |
| | Gluteal Injection | First Thigh Injection | Last Thigh Injection | | | | | | | | | | | | | | | |
| Q8W | Week -8 to Day 1 | Day 1 to Week 8 | Week 8 to Week 16 | | | | | | | | | | | | | | | |
| Q4W | Week -4 to Day 1 | Day 1 to Week 4 | Week 12 to Week 16 | | | | | | | | | | | | | | | |
| Evaluable Concentration | | | | | | | | | | | | | | | | | | |

Pharmacokinetic Analyses

PK concentration will be summarized in two ways: 'all data' without regard to timing relative to scheduled time and 'evaluable data'.

The 'evaluable data' are from the samples that met sample collection window criteria. Sampling windows are set relative to the previous dose as follows:

- 20-28 hrs after last oral dose taken and properly administered last 3 oral doses for pre-dose sample at Week 4B for participants requiring oral lead-in
- ± 4 days for pre-dose sample at visits other than Week 4B, and for pre-dose samples at Week 4B for participants not requiring oral lead-in (e.g. participants transitioning from ATLAS Q4W and remain on Q4W arm in this study)
- 3-10 days post last injection for 1-week post injection visits
- 21-35 days post last injection for 4-week post-dose samples (e.g. collected at sub-study Week -4, Week 4 and Week 12 visits). Note that 4-week post-dose samples will be collected from subjects on Q8W arm only.
- 1-3 hours post last injection for 2-hour post-dose samples
- Samples impacted by dosing errors (wrong dose) or oral bridging will also be excluded

| Timepoint | Evaluable Window | For Programming: |
|---|--|--|
| Pre-dose: WK4B for participants requiring oral lead-in | 20-28 hrs after last oral dose taken and the last 3 oral doses administered properly | 20 hrs \leq Time since Last Oral Dose \leq 28 hrs and the last 3 oral doses administered on the three consecutive days prior to WK4B. |
| Pre-dose at other visits, Pre-dose WK4B for participants not requiring oral lead-in | ± 4 days | For Q4W arm, Day 1 pre-dose, Week 8 for those transitioning from SOC (i.e. requiring oral lead-in), and the immediate next visit after reloading on Q8W arm: 24 days \leq Days Since Last Injection \leq 32 days For visits other than above on Q8W arm: 52 days \leq Days Since Last Injection \leq 60 days |
| 1-WK-Post: | 3-10 days post last injection | 3 days \leq Days Since Last Injection \leq 10 days |
| 4-WK-Post: | 21-35 days post last injection | 21 days \leq Days Since Last Injection \leq 35 days |
| 2-HR-Post: | 1-3 hours post last injection | 1 hr \leq Time since Last Oral Dose \leq 3 hrs |

Relative Time is calculated relative to the date and time of last dose. For example, if the time of the last dose (e.g. oral lead-in/oral bridging) is missing, then the relative time for PK sample will be set to missing and the sample will not be considered 'evaluable'.

Pharmacokinetic Analyses

If a pre-dose sample is collected on the same day as the first dose of oral bridging, the time of the first dose (not recorded in eCRF) is assumed to be 'after' the collection of pre-dose sample, unless medical monitor or Data querying informs otherwise.

The time-deviation (hours) from the targeted timepoint will be calculated for the post-dose samples using the following formula:

Time_deviation (hrs) for '2-Hour POST' = Sample date.time - last injection date.time - 2 hours

Time_deviation (hrs) for '1-Week POST' = Sample date.time - last injection date.time - 7*24 hours

Time_deviation (hrs) for '4-Week POST' = Sample date.time - last injection date.time - 28*24 hours

The following windows are for defining 'evaluable' Long-term Follow-up phase PK concentrations.

| Timepoint | Evaluable Window | For Programming: |
|-----------------|------------------|---|
| LTFU MONTH 1/WD | ± 4 days | 24 days ≤ Days Since Last Injection ≤ 32 days |
| LTFU MONTH 3 | ± 1 Weeks | 77 days ≤ Days Since Last Injection ≤ 91 days |
| LTFU MONTH 6 | ± 2 Weeks | 154 days ≤ Days Since Last Injection ≤ 182 days |
| LTFU MONTH 9 | ± 2 Weeks | 238 days ≤ Days Since Last Injection ≤ 266 days |
| LTFU MONTH 12 | ± 2 Weeks | 322 days ≤ Days Since Last Injection ≤ 350 days |

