| 
 Following Log_e-transformation, PK parameters will be separately analyzed by treatment arm and analyte using a mixed effects model with dosing interval (gluteal injection, first thigh injection and last thigh injection) as fixed effects and subject as random effects. In each model, only subjects with evaluable PK parameter estimates in both dosing intervals are included. For example, in the model for comparing C_{max} estimated from the first CAB thigh |

| |
|--|
| injection interval with Cmax estimated from the gluteal injection interval among Q8W subjects, only the Q8W subjects with evaluable Cmax estimates from both first CAB thigh injection interval and gluteal injection interval are included. |
| Model Checking & Diagnostics |
| 
Model assumptions will be applied, but appropriate adjustments may be made based on the data. |
| Model Results Presentation |
| 
The estimated difference and 90% CI obtained on the \log_e scale will be exponentiated to provide an estimate of geometric mean ratio and its associated 90% CI. The estimate of within-subject variability (%CVw) will also be provided. |

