| CD4+ cell count | X | | X | | X | X | X | | X | | | X | |
| CD8+ cell count | | | X | | | | | | | X | | | |
| Urinalysis ^f | | | X | | | | | | | X | | | |
| Fasting lab assessments: Glucose, Cholesterol (Total, HDL and LDL) and triglycerides ^g | | | X | | | | | | X | | | | |
| PBMC for storage | | | X | | | | | | | | | | |

| Procedure | Screening Phase ^d Gluteal administration | | Thigh Injection Phase ^d Q4 Weekly thigh administration | | | | | | Return to Gluteal Injection Phase ^d Q4 Weekly gluteal admin. | | | |
|--|---|---------|---|--------|--------|--------|---------|---------|---|---------|---------|---------|
| | Screening (Week -4) | Week -3 | Day1 | Week 1 | Week 4 | Week 8 | Week 12 | Week 13 | Week 16 | Week 17 | Week 20 | Week 24 |
| PK sample collection^j | | | | | | | | | | | | |
| Pre dose PK sampling | X | | X | | X | X | X | | X | | | |
| 2h Post dose PK sampling | | | X | | X | X | X | | | | | |
| Post dose PK sampling (~Cmax) | | X | | X | | | | | X | | X | |
| PROs^l | | | | | | | | | | | | |
| HIVTSQc | | | | | | | | | X ^k | | | |
| HIVTSQs | | | X | | | | | | X ^k | | X | |
| NRS^h | X | X | X | X | | | X | X | X | X | | |
| Preference Thigh inj. vs Gluteal inj. | | | | | | | X | | | | X | |

- a. Physical exams should be conducted as part of normal routine clinical care. Medical assessments include any decisions the study staff must make for participants management and/or care of participant.
- b. Measure vital signs after about 5 minutes of rest in a semi-supine position.
- c. A 12-lead ECG will be performed after resting in a semi-supine position for at least 5 minutes. ECGs will be performed pre-dose. A 2-hour post dose ECG will also be performed at sub-study Day1 visit.
- d. All injection visits during the sub-study should kept to the same projected visit schedule as in the parent study.
- e. Women of childbearing potential only. SR=serum, UR=urine. Urine pregnancy test can be performed at study visits when other blood draws are not required in order to limit needle sticks.
- f. A morning specimen is preferred.
- g. An overnight fast is preferred; however, a minimum of a 6-hour fast is acceptable.
- h. Should be collected 30 to 60 minutes post injection

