|--|---|------------|------------|---|-----------|-----------|--------|-----------|------------|---|------------|---------|
| | Screening (Week -8) | Week -7 | Week -4 | Day1 | Week 1 | Week 4 | Week 8 | Week 9 | Week 12 | Week 16 | Week 17 | Week 24 |
| | HDL and LDL) and triglycerides ^g | | | | | | | | | | | |
| PBMC for storage | | | | X | | | | | | | | |
| PK samples^j | | | | | | | | | | | | |
| Pre dose PK sampling | X | | | X | | | X | | | X | | |
| 2h Post dose PK sampling | | | | X | | | X | | | | | |
| Post dose PK sampling (-Cmax) | | X | X | | X | X | | X | X | | X | |
| PROs^l | | | | | | | | | | | | |
| HIVTSQc | | | | | | | | | | X ^k | | |
| HIVTSQs | | | | X | | | | | | X ^k | | X |
| NRS^h | X | X | | X | X | | X | X | | X | X | |
| Preference Thigh inj. vs Gluteal inj. | | | | | | | X | | | | | X |

- a. Physical exams should be conducted as part of normal routine clinical care. Medical assessments include any decisions the study staff must make for participants management and/or care of participant.
- b. Measure vital signs after about 5 minutes of rest in a semi-supine position.
- c. A 12-lead ECG will be performed after resting in a semi-supine position for at least 5 minutes. ECGs will be performed pre-dose. A 2-hour post dose ECG will also be performed at sub-study Day1 visit.
- d. All injection visits during the sub-study should kept to the same projected visit schedule as in the parent study.
- e. Women of childbearing potential only. SR=serum, UR=urine. Urine pregnancy test can be performed at study visits when other blood draws are not required in order to limit needle sticks.
- f. A morning specimen is preferred.
- g. An overnight fast is preferred; however, a minimum of a 6-hour fast is acceptable.
- h. Should be collected 30 to 60 minutes post injection
- i. Week 24 IM administration will not be considered part of the sub-study assessments. The IM administration at W24 and any assessments completed after IM administration at this visit will be considered part of the parent study.
- j. PK window allowed for sample collection: For 1-week post dose sample (3 to 10 days post dose), for 4-week post dose sample (+-7 days) and for 2-hours post dose samples (\pm 1 hour)
- k. At Week 16, HIVTSQs should be administered before HIVTSQc.

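### Sub-study: Cmax and AUC are compared between thigh and gluteal injections on unmatched sampling, because only the thigh intervals have a 2-hour sample

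*SAP*

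**What the plan says.** The thigh-versus-gluteal comparison of Ctau, post-dose concentrations (~Cmax) and AUC is a primary sub-study endpoint (SAP 2.2.1).

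Section 15.6.5 defines the parameters: "The following PK parameters will be determined from the sub-study concentration-time data for each treatment, analyte and dosing interval". They are Cmax, tmax and AUC(0-tau), obtained by standard non-compartmental analysis (NCA), and "All calculations of non-compartmental parameters will be based on actual sampling times". Ctau is taken separately, from the pre-dose sample that opens the next interval. The intervals are one gluteal (Week -8 or Week -4 to Day 1), the first thigh and the last thigh.

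Section 9.3 fits a mixed model to the log parameters with "dosing interval (gluteal injection, first thigh injection and last thigh injection) as fixed effects and subject as random effects" and reports geometric mean ratios with 90% confidence intervals. The figure list (15.15.7.7) names the contrasts as first thigh against gluteal and last thigh against gluteal.

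The 2-hour sampling row reads "Post dose PK sampling | | | | X | | | X" for Q8W (15.2.4) and "Post dose PK sampling | | | X | | X | X | X" for Q4W (15.2.3). The Q4W columns begin "Screening (Week -4) | Week -3 | Day1 | Week 1 | Week 4".

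**The concern.** The 2-hour sample is an extra observation in the thigh intervals with no gluteal counterpart. An NCA Cmax is the highest observed value, so the thigh Cmax is a maximum over one more sample. In the AUC, the first segment up to 1 week passes through the 2-hour value after a thigh injection, but runs straight from pre-dose to 1 week after the gluteal one. The model cannot separate this sampling difference from an effect of injection site. Comparing first with last thigh does not reveal it, because both contain the sample. An artefact that raises the thigh values could hide a real reduction in peak or total exposure after thigh injection.

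**Working it through.** **1. Which visits carry the 2-hour sample.**
- Q8W columns run Week -8, -7, -4, Day 1, Week 1, 4, 8 and so on. The marks fall in the 4th and 7th: Day 1 and Week 8, both thigh injections.
- Q4W columns run Week -4, -3, Day 1, Week 1, 4, 8, 12 and so on. The marks fall in the 3rd, 5th, 6th and 7th: Day 1 and Weeks 4, 8 and 12, all thigh injections. Only Day 1 and Week 12 open an analysed interval.

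Nominal samples per interval, counting the pre-dose sample at each end and a 1-week sample:

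| Arm | Gluteal | Thigh |
|---|---|---|
| Q4W | 3 | 4 |
| Q8W (adds a 4-week sample) | 4 | 5 |

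**2. Assumptions.** The SAP gives no concentrations and no precision figure for this comparison, so there is nothing to reproduce. Take identical true profiles at both sites, so the true ratio is 1. Set pre-dose and end-of-interval level = 1, 1-week level = P (1.2 to 2.0), and 2-hour level = k (0.9 to 2.0). For simulation, add independent log-normal error to each sample, CV 0 to 30%.

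**3. AUC.** By the linear trapezoid, the extra point changes the area by 0.5 × 7 × (k − L) days. L is the height at 2 hours of the straight line from pre-dose to 1 week: L = 1 + (P − 1) × (2/24)/7. If the decline after 1 week is also straight, AUC = (tau/2)(1 + P), with tau = 28 or 56 days. The relative change is then (7/tau)(k − L)/(1 + P).

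Example, Q4W, P = 1.2, k = 2: L = 1.0024, and 0.25 × 0.9976/2.2 = 11.3%.

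| k | Q4W, P = 1.2 | Q4W, P = 2.0 | Q8W, P = 1.2 | Q8W, P = 2.0 |
|---|---|---|---|---|
| 0.9 | −1.2% | −0.9% | −0.6% | −0.5% |
| 1.0 | −0.03% | −0.1% | −0.01% | −0.05% |
| 1.5 | +5.7% | +4.1% | +2.8% | +2.0% |
| 2.0 | +11.3% | +8.2% | +5.7% | +4.1% |

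The sign follows k − L. Simulated error moves these little: ratios run from about 0.99 to 1.12 (Q4W) and 0.99 to 1.06 (Q8W).

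**4. Cmax.** The maximum over a set plus one point cannot be below the maximum over the set. Without error the ratio is max(P, k)/P. It is 1 while k ≤ P, 1.5/1.2 = 1.25 at k = 1.5 and P = 1.2, and 2/1.2 = 1.67 at k = 2 and P = 1.2. With error:
- k well below P (0.9 or 1.0 against 2.0): 1.00.
- k moderately below P (1.2 against 1.5), CV 30%: 1.03 (Q8W) to 1.05 (Q4W).
- k = P = 1.2: 1.04 to 1.06 at CV 15%, 1.06 to 1.09 at CV 30%.
- k = P = 2.0: 1.08 to 1.09 at CV 15%, 1.12 (Q8W) to 1.17 (Q4W) at CV 30%.

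**5. Scale.** With 41 pairs per arm (SAP 2.3) and an assumed within-subject log SD of 0.25, the 90% half-width is 1.684 × 0.25 × √2/√41 = 0.093 on the log scale, about 9 to 10%.

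**6. After matching.** With the 2-hour sample left out of the thigh intervals, both ratios return to 1.00 in every setting (0.997 to 1.003, simulation error).

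**The case against.** A reader might infer that the schedule biases both ratios upward, so that thigh exposure would look higher even with identical sites. The documents do not support that. For AUC the sign depends on an unknown 2-hour level, and at or just below pre-dose the effect is nil or slightly negative. For Cmax only the direction is fixed, and the effect may be nil.

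Other points for the plan have some force:
- Both schedules label the roughly 1-week row as ~Cmax and list the 2-hour sample separately, which suggests that the planners expect the peak later. If so, the Cmax effect sits near zero. However, 15.6.5 defines the analysed Cmax as the NCA maximum, not the 1-week value.
- The analysis is estimation only. The SAP sets no margin or decision rule for these ratios.
- By-visit summaries, tmax and the subject listing would let a careful reader see the imbalance. NCA also follows working practices not shown. None of this gives a pre-specified matched ratio.
- The evaluability table in 15.6.5 ties its programming rule for the 2-hour sample to the last oral dose, although the window itself refers to the last injection. Read literally, the rule could make the sample non-evaluable. Evaluability is applied explicitly only to Ctau, so this does not clearly remove the sample from the NCA.
- In the supplied text the Q4W ~Cmax row appears shifted (marks under Weeks 16 and 20 rather than 13 and 17), possibly from PDF extraction. The Q8W table is the safer evidence.
- Dropping the 2-hour sample altogether would discard a genuine early thigh peak. That is a fair reason to keep both versions.

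**Conclusion.** The concern holds as a lack of comparability. Followed as written, two of the three primary PK ratios confound injection site with sampling scheme. The schedules and sections 15.6.5 and 9.3 establish the mismatch and the direction for Cmax (unchanged or upward). They do not establish the direction for AUC or the size of either effect, which rest on the assumed levels and error above. Within those assumptions the artefact ranges from negligible to about the width of the confidence limits, and beyond it for Cmax if the 2-hour level exceeds the 1-week level. Ctau comes from pre-dose samples and is unaffected.

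**What to change.** In 15.6.5 and 9.3, pre-specify that Cmax and AUC(0-tau) for the thigh-versus-gluteal ratios are also derived from the nominal times common to all three intervals: pre-dose, 1 week, 4 weeks for Q8W, and end of interval. Base the site comparison on these matched ratios. Report the thigh values that include the 2-hour sample alongside, so that an early thigh peak stays visible. In the same edit, say whether ~Cmax in 2.2.1 means the NCA maximum or the 1-week concentration, and make the 2-hour programming rule agree with its window.

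No new samples are needed. The cost is one extra NCA run and one extra set of tables.

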- i. Week 24 IM administration will not be considered part of the sub-study assessments. The IM administration at W24 and any assessments completed after IM administration at this visit will be considered part of the parent study.
- j. PK window allowed for sample collection: For 1-week post dose sample (3 to 10 days post dose), for 4-week post dose sample (+-7 days) and for 2-hours post dose samples (± 1 hour)
- k. At Week 16, HIVTSQs should be administered before HIVTSQc.
- l. All Patient Report Questionnaires/Surveys - except NRS - will be administered via paper instrument (in exceptional circumstances the questionnaires could be completed via telephonic interview, please refer to COVID19 appendix for additional details) at the beginning of the visit before any other assessments are conducted.

Note: There is a typo in the schedule of events table where weight and BMI will be collected at Week -4 visit instead of Day 1 visit.

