 - Exposure to CAB LA + RPV LA = Number of IP injection visits received during Thigh Injection Phase. Note that the planned Sub-study Week 16 injections belong to Return to Gluteal Injection Phase.
 - The SOC or CAB+RPV oral bridging are not allowed in this phase.
 - Overall exposure to IP:

For participants on Q4W arm: min [Date of Latest Thigh Injection Phase Visit up to the Nominal Sub-study Week 16 Visit Date, max (Date of Last Injection + 35, Date of Last Dose of Oral CAB+RPV, Date of Last Dose of SOC Oral Bridging)] – Date of First Thigh Injection) + 1

For participants on Q8W arm: min [Date of Latest Thigh Injection Phase Visit up to the Nominal Sub-study Week 16 Visit Date, max (Date of Last Injection + 63, Date of Last Dose of Oral CAB+RPV, Date of Last Dose of SOC Oral Bridging)] – Date of First Thigh Injection + 1

Note that the Nominal Sub-study Week 16 visit date is defined in Section [15.6.1](#).
 - Overall exposure to IP = Overall exposure to Study Treatment.
- For Thigh Injection + Return to Gluteal Injection Phase
 - Exposure to CAB LA + RPV LA = Number of IP injection visits received during Thigh Injection or Return to Gluteal Injection Phase. Note that the injections received on the date of Sub-study Week 24 visit belong to the Extension Phase in main study.
 - The SOC or CAB+RPV oral bridging are not allowed in these two phases.
 - Overall exposure to IP:

For participants on Q4W arm: min [End of Sub-study Date, max (Date of Last Injection + 35, Date of Last Dose of Oral CAB+RPV, Date of Last Dose of SOC Oral Bridging)] – Date of First Thigh Injection) + 1

For participants on Q8W arm: min [End of Sub-study Date, max (Date of Last Injection + 63, Date of Last Dose of Oral CAB+RPV, Date of Last Dose of SOC Oral Bridging)] – Date of First Thigh Injection + 1

Note that the End of Sub-study Date is defined in Section [15.6.1](#).
 - Overall exposure to IP = Overall exposure to Study Treatment.
- Last Injection and/or Last Dose of Oral CAB+RPV and/or Last Dose of SOC Oral Bridging are only applicable to those who permanently discontinued study treatment.

| Other Safety Endpoints |
|--|
| 
 Duration of dosing in participant years will be calculated as the sum of participant duration of dosing in days (across all participants)/365.25 Participants who were randomized but did not report an IP start date will be categorised as having zero days of exposure. |
| Adherence to CAB/RPV Injection Schedule |

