15.15.7.4. Safety Tables

| Safety Tables | | | | | |
|-----------------|------------------|------------------------|--|--|-------------|
| No. | Population | IDSL / Example Shell | Title | Programming Notes | Deliverable |
| Exposure | | | | | |
| 3.1 | Sub-study Safety | 207966/primary_34/T3.1 | Summary of Extent of Exposure to Study Treatment (Thigh Injection + Return to Gluteal Injection Phase) | Include both continuous and categorical summaries for Exposure (No. of Thigh Injection Visits), Exposure (No. of Return to Gluteal Injection Visits), Exposure (No. of Injection Visits), Overall Exposure to Study Treatment during the Thigh Injection Phase, Overall Exposure to Study Treatment during the Thigh Injection + Return to Gluteal Injection Phase. The levels for categorical summaries will be selected as appropriate. Remove the footnote. | Sub-study |
| 3.2 | Sub-study Safety | 207966/primary_34/T3.2 | Summary of Needle Length and Gauge for CAB Injection (Thigh Injection Phase) | Replace the "at Maintenance + Extension Phase" in footnote with "during the Thigh Injection phase". | Sub-study |
| 3.3 | Sub-study Safety | 207966/primary_34/T3.3 | Summary of Needle Length and Gauge for RPV Injection (Thigh Injection Phase) | Replace the "at Maintenance + Extension Phase" in footnote with "during the Thigh Injection phase". | Sub-study |
| 3.4 | Sub-study Safety | 207966/primary_34/T3.4 | Summary of Adherence to CAB/RPV Injection Dosing Schedule (Thigh Injection Phase) | Remove the missed Injection related rows from shell. Add "Missed Injection" row. Replace the footnote with "[1] The total number of expected thigh injection visits following the first thigh injection." Add a footnote "Note: Oral bridging is not allowed in the sub-study." | Sub-study |

| Safety Tables | | | | | |
|----------------|------------------|-------------------------|--|---|-------------|
| No. | Population | IDSL / Example Shell | Title | Programming Notes | Deliverable |
| 3.5 | Sub-study Safety | 207966/primary_34/T3.4 | Summary of Adherence to CAB/RPV Injection Dosing Schedule (Thigh Injection + Return to Gluteal Injection Phase) | Remove the missed Injection related rows from shell. Add "Missed Injection" row. Replace the footnote with "[1] The total number of expected injection visits in sub-study following the first thigh injection." Add a footnote "Note: Oral bridging is not allowed in the sub-study.". | Sub-study |
| Adverse Events | | | | | |

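### The programming rule for evaluable 2-hour PK samples is tied to the last oral dose instead of the last injection; coded as written, no sub-study 2-hour sample could be evaluable

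*SAP*

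**What the plan says.** SAP Section 15.6.5, under Evaluable Concentration, sets sampling windows relative to the previous dose. It gives them first as a list and then as a table with one column for the window and one for programming.

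- The list gives "1-3 hours post last injection for 2-hour post-dose samples".
- The window cell of the 2-HR-Post row repeats the 1 to 3 hour, injection-based rule.
- The programming cell of that row keeps the limits of 1 and 3 hours but applies them to "Time since Last Oral Dose". The same variable appears correctly in the row for the Week 4B pre-dose sample after oral lead-in.
- Below the table, the deviation from target is defined as "Time_deviation (hrs) for '2-Hour POST' = Sample date.time - last injection date.time - 2 hours".
- In the sub-study schedules (Sections 15.2.3 and 15.2.4) the row "2h Post dose PK sampling" is marked only at thigh injection visits. The window in the footnote is "and for 2-hours post dose samples (± 1 hour").
- For the thigh injection phase, Section 15.6.4 states: "The SOC or CAB+RPV oral bridging are not allowed in this phase". A footnote specified in the sub-study safety tables (Section 15.15.7.4) says the same of the whole sub-study: "Oral bridging is not allowed in the sub-study".

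**The concern.** The programming column is the text from which code is written and checked, so its content is an operative rule. Here it names a reference event that does not occur at the visits to which the row applies. A thigh-phase participant who follows the plan takes no oral study drug, so the last oral dose is remote, absent or untimed. A sample drawn exactly on target would still fail the test.

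At stake are the evaluable-data displays of the sub-study: Tables 4.3 and 4.4 (CAB and RPV concentrations by visit) and Figures 4.3 to 4.6 (mean and median concentration-time plots). The sub-study figure list contains mean and median plots for evaluable concentrations only, so the 2-hour point would be missing from every summary concentration-time figure.

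**Working it through.** **Inputs**

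- Schedule window: 2 hours ± 1 hour after dosing (Sections 15.2.3 and 15.2.4, footnote j).
- 2-hour visits: Q4W at sub-study Day 1 and Weeks 4, 8 and 12 (4 occasions); Q8W at Day 1 and Week 8 (2 occasions).
- Planned size: about 82 participants, 41 per arm, enrolled after at least 152 weeks in the main study (Section 2.3).
- Oral dosing: lead-in ends at Week 4B; oral bridging is not allowed in the thigh injection phase.
- If the time of the last dose is missing, the relative time is set to missing and the sample is not evaluable (Section 15.6.5).

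**Step 1. Reproduce the intended window.** 2 − 1 = 1 hour and 2 + 1 = 3 hours after the injection. This agrees with the list and with the window cell.

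**Step 2. Apply the programming cell literally** (1 ≤ hours since last oral dose ≤ 3) to a sample drawn 2 hours after the Day 1 thigh injection.

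| Last oral dose | Hours since that dose | Within 1 to 3 h? |
|---|---|---|
| Oral lead-in only | at least (152 − 4) × 168 + 2 = 24,866 | No |
| Bridging assumed to end at the Q4W screening injection (Week −4) | 4 × 168 + 2 = 674 | No |
| Bridging assumed to end at the Q8W screening injection (Week −8) | 8 × 168 + 2 = 1,346 | No |
| No oral dose in this study, or its time missing | missing | No |

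The two bridging rows are a deliberately generous assumption about how recent a bridging dose could be. At later thigh visits the gap only grows. If a prohibited bridging dose were taken during the phase, a separate rule applies: "Samples impacted by dosing errors (wrong dose) or oral bridging will also be excluded".

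**Step 3. Count the occasions exposed.** Q4W 41 × 4 = 164; Q8W 41 × 2 = 82; total 246 planned occasions per analyte. None can pass.

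**Step 4. Apply the same limits to time since the last injection.** A sample on target gives 2 hours, which lies within 1 to 3. Every sample drawn inside the schedule's window passes, apart from those removed for dosing errors.

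**Step 5. Trace what uses the evaluable flag.** Tables 4.3 and 4.4 and Figures 4.3 to 4.6 are restricted to evaluable concentrations. Tables 4.1 and 4.2, the individual plots (Figures 4.1 and 4.2) and Listings 21 and 22 are not. Ctau comes from a pre-dose sample. Cmax and AUC(0-tau) come from non-compartmental analysis on actual sampling times, and Section 15.6.5 does not say that this analysis takes only evaluable concentrations.

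**The case against.** The intended rule is not in doubt. The list, the neighbouring cell, the deviation formula and the schedule footnote all point to the injection. The odd cell looks like a carry-over from the Week 4B oral lead-in row. A programmer may well notice, and evaluable tables with no data at a scheduled timepoint would prompt a query, so the error would show itself instead of quietly biasing a result. The count of 246 is also a ceiling.

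All of this stands, and it makes the consequence conditional on the cell being coded literally. It does not make the cell right. A programmer who follows the window column departs from the written programming rule, and one who follows the programming column empties a timepoint.

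A reader might go further and infer that the 2-hour data would be lost, or that the thigh versus gluteal PK comparison is compromised. The SAP does not support either. The values remain in the all-data tables, individual plots and listings, and no link from the evaluable flag to Cmax or AUC(0-tau) is stated. A reader might also suppose that the 2-hour samples were added to capture an early peak. The SAP gives no reason for them, and the schedules attach the approximate-Cmax label to a different row of post-dose samples.

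**Conclusion.** The cell is wrong as written and contradicts its own row. If programmed literally, 0 of up to 246 planned 2-hour occasions per analyte could be evaluable, and the 2-hour timepoint would be empty in the evaluable CAB and RPV tables and in the mean and median figures of the sub-study. The count assumes 41 participants per arm and complete attendance. The finding that none passes rests on the plan's own ban on oral bridging at those visits and its handling of missing dose times. The damage is confined to descriptive displays; no effect on Ctau, Cmax or AUC(0-tau) is established.

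**What to change.** In Section 15.6.5, in the programming cell of the 2-HR-Post row, replace the last oral dose with the last injection, so that the condition is 1 hr ≤ time since last injection ≤ 3 hrs. Compute it from the injection date and time recorded in the eCRF, which the deviation formula in the same section already uses. The cost is one table cell and a check that the evaluability code follows it. No new data, design change or clinical decision is needed.
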